The protocol, informed consent form(s), recruitment materials, and all participant materials will be submitted to the IRB for review and approval. Approval of both the protocol and the consent form must be obtained before any participant is enrolled. Any amendment to the protocol will require review and approval by the IRB before the changes are implemented to the study. All changes to the consent form will be IRB approved; a determination will be made regarding whether a new consent needs to be obtained from participants who provided consent, using a previously approved consent form.

1 PROTOCOL SUMMARY

1.1 SYNOPSIS

Title:	The CAffeine, Postoperative delirium, And CHange IN Outcomes after Surgery-2 (CAPACHINOS-2) Study
Study Description:	The objective of this study is to test the effects of caffeine on neurocognitive and clinical recovery after major surgery. Specifically, this trial tests the primary hypothesis that caffeine will reduce the incidence of postoperative delirium.
Objectives:	
Primary objective: The primary objective is to determine whether postoperative caffeine reduces the incidence of postoperative delirium, based on standardized delirium assessment methodology.
 
Secondary Objectives: To determine (1) whether caffeine improves postoperative patient satisfaction, based on validated, patient-reported quality of recovery measures, and (2) neural correlates of delirium and Mild Cognitive Impairment, based on advanced electroencephalographic (EEG) analysis.

Endpoints:	
Primary Endpoint: Incidence (%) of postoperative delirium, measured via long-form Confusion Assessment Method (CAM).¹
 
Secondary Endpoints:
 
-- Delirium severity (CAM-S)²-- Delirium duration (days, n)-- Patient-reported 15-item Quality of Recovery score³-- Agitation (via Richmond Agitation and Sedation Scale, RASS)⁴-- Sedation (via Richmond Agitation and Sedation Scale, RASS)⁴-- Headache severity (10-centimeter visual analog scale, VAS)-- Cumulative opioid consumption (oral morphine equivalents, mg)

The CAffeine, Postoperative Delirium, And CHange IN Outcomes after Surgery-2 (CAPACHINOS-2) Study Protocol <2.0>

[figure not shown]
Version <2.0>
<14 December 2022>

Study Population:	In total, surgical patients (n=250; ≥70 years of age) presenting for major non-cardiac, non-intracranial neurologic surgery will be recruited at Michigan Medicine.
Phase:	2
Description of Sites/Facilities Enrolling Participants:	Study operations will be conducted at Michigan Medicine University Hospital and Cardiovascular Center; Ann Arbor, MI USA.
Description of Study Intervention:	This will be a three-arm parallel trial. Participants will be randomized to intravenous dextrose 5% in water (placebo), low-dose caffeine citrate (1.5 mg/kg), or high-dose caffeine citrate (3 mg/kg) at multiple postoperative time points over a 30-minute infusion period.
Study Duration:	The estimated trial duration will be approximately four years.
Participant Duration:	Total study duration for patients will be approximately 30 days.

The Caffeine, Postoperative Delirium, And CHange IN Outcomes after Surgery-2 (CAPACHINOS-2) Study Protocol <2.0>

Version <2.0>
<14 December 2022>

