4 STUDY DESIGN

4.1 OVERALL DESIGN

The **central hypothesis** of this study is that intravenous caffeine will reduce the incidence of postoperative delirium. This will be a Phase II, single-center, quadruple-blinded, placebo-controlled, block-randomized trial. Written informed consent will be obtained from all participants, and institutional review board approval will be obtained. The trial will follow a parallel design, and participants will be block-randomized with a 1:1:1 allocation ratio (placebo: 1.5 mg/kg caffeine: 3 mg/kg caffeine).

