6.1.2 DOSING AND ADMINISTRATION

The study drug will be administered as an intravenous infusion, using an infusion pump, over 30 (±5) minutes beginning during surgical closure and on the first two postoperative mornings. Low-dose caffeine will consist of 1.5 mg/kg caffeine base, and high-dose caffeine will contain 3 mg/kg caffeine base; both caffeine drugs will be dissolved in 40 mLs of dextrose 5% in water. No dose or timing changes are anticipated, and the infusion will be administered over the entire 30 (±5) minutes. A research nurse or physician assistant will oversee the drug administration and monitor blood pressure (every 5 minutes), heart rate, heart rhythm (via 5-lead electrocardiography), and continuous pulse oximetry.

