6.2.2 FORMULATION, APPEARANCE, PACKAGING, AND LABELING

Per manufacturer (Fresenius Kabi USA, LLC) package insert: Caffeine citrate injection is indicated for the treatment of apnea of prematurity (<https://dailymed.nlm.nih.gov/dailymed/drugInfo.cfm?setid=38b39044-737a-4247-a6c4-c86f5e92490e&audience=consumer>). Caffeine citrate injection, USP for intravenous administration is a clear, colorless, sterile, nonpyrogenic, preservative-free, aqueous solution adjusted to pH 4.7. Each mL contains 20 mg caffeine citrate (equivalent to 10 mg of caffeine base) prepared in solution by the addition of 10 mg caffeine anhydrous to 5 mg citric acid monohydrate, 8.3 mg sodium citrate dihydrate and Water for Injection, USP. Caffeine, a central nervous system stimulant, is an odorless white crystalline powder or granule, with a bitter taste. It is sparingly soluble in water and ethanol at room temperature. The chemical name of caffeine is 3,7-dihydro-1,3,7-trimethyl-1H-purine-2,6-dione. In the presence of citric acid it forms caffeine citrate salt in solution. Vials should and will be inspected visually for particulate matter prior to use.

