6.2.4 PREPARATION

The assigned caffeine citrate dose will be diluted in dextrose 5% in water to a total volume of 40 mL. These procedures will occur via standard Michigan Medicine Research Pharmacy protocols, procedures, and operations.

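### The synopsis gives the active doses as mg/kg of caffeine citrate and section 6.1.2 gives the same numbers as mg/kg of caffeine base, a twofold difference by the protocol's own conversion

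*Protocol*

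**What the plan says.** - **Section 1.1, Synopsis.** The active arms are "low-dose caffeine citrate (1.5 mg/kg), or high-dose caffeine citrate (3 mg/kg"). The mg/kg figure follows directly on the name of the salt.
- **Section 6.1.2, Dosing and Administration.** "Low-dose caffeine will consist of 1.5 mg/kg caffeine base, and high-dose caffeine will contain 3 mg/kg caffeine base".
- **Section 6.2.2, Formulation.** "Each mL contains 20 mg caffeine citrate (equivalent to 10 mg of caffeine base"). This is the only citrate-to-base conversion in the protocol.
- **Section 6.2.4, Preparation.** "The assigned caffeine citrate dose will be diluted in dextrose 5% in water to a total volume of 40 mL". It gives no mg/kg figure and does not mention the base.
- **Section 4.1, Overall Design.** "1:1:1 allocation ratio (placebo: 1.5 mg/kg caffeine: 3 mg/kg caffeine"). Neither salt nor base is specified.

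Sections 4.3 (dose justification), 5.2 (the 130 kg exclusion) and 6.3 (randomization) also use 1.5 and 3 mg/kg, or 3 mg/kg alone, without saying whether citrate or base is meant.

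**The concern.** A mg/kg dose of caffeine citrate and the same mg/kg dose of caffeine base are different amounts of drug. The synopsis and the dosing section use the same two numbers for different substances, and both are current text. A reader who works from the synopsis and one who works from section 6.1.2 would specify different infusions for the same participant.

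The discrepancy concerns what the intervention is. It bears on exposure in a population aged 70 and over, and on how the results would be described, since a report of an effect at 3 mg/kg is not interpretable until the unit is known. The two readings also overlap: the high dose on one is the low dose on the other.

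**Working it through.** **Inputs, all from the protocol**
- Dose figures: 1.5 and 3 mg/kg, as citrate (section 1.1) or as base (section 6.1.2).
- Product strength: 20 mg citrate per mL, equivalent to 10 mg base per mL (section 6.2.2).
- Weight limit: 130 kg (section 5.2).

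**Step 1: conversion ratio.** 20 / 10 = 2 mg citrate per mg base. This agrees with the 10 mg of anhydrous caffeine per mL listed in the same section.

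**Step 2: both readings in both units.** Base = citrate / 2; citrate = base × 2.

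| Arm | Synopsis reading: citrate | Synopsis reading: base | Section 6.1.2 reading: base | Section 6.1.2 reading: citrate |
|---|---|---|---|---|
| Low | 1.5 mg/kg | 1.5 / 2 = 0.75 mg/kg | 1.5 mg/kg | 1.5 × 2 = 3 mg/kg |
| High | 3 mg/kg | 3 / 2 = 1.5 mg/kg | 3 mg/kg | 3 × 2 = 6 mg/kg |

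The ratio between readings is 2 in each arm. The synopsis high dose and the section 6.1.2 low dose are both 1.5 mg/kg base.

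**Step 3: amount per infusion, high-dose arm.** Stock volume = mg base / 10.

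| Weight | Section 6.1.2 reading | Synopsis reading |
|---|---|---|
| 80 kg (assumed, for illustration) | 3 × 80 = 240 mg base, 24 mL | 1.5 × 80 = 120 mg base, 12 mL |
| 130 kg (limit in section 5.2) | 3 × 130 = 390 mg base, 39 mL | 1.5 × 130 = 195 mg base, 19.5 mL |

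**Step 4: does another section settle it?**
- Sections 4.1, 4.3 and 6.3 fit either reading, because they do not name the moiety.
- Section 5.2 ties the 130 kg limit to a 3 mg/kg dose coming close to a recommended daily maximum. The protocol gives no figure for that maximum and no unit for the dose, so it cannot decide between 195 and 390 mg base.
- Section 9.2 cites a preliminary dose range of 1.7 to 4.5 mg/kg (median 2.5), again without salt or base.
- Section 6.2.4 names the citrate dose but gives no amount, so it neither contradicts section 6.1.2 nor resolves the question.

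**The case against.** The strongest reply is that the synopsis is only a summary, that caffeine citrate is the product name used across the protocol, and that its parentheses can be read as product plus dose. Section 6.1.2 is the dosing section and the only place that deliberately fixes the moiety, for both arms. An editorial slip in the synopsis is therefore plausible. That stands as a likely explanation, but it leaves two current statements that differ twofold, and the protocol has no rule saying which one governs.

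It is also fair to say that within either reading the two active arms keep their 1:2 ratio, so the randomized comparison is not undermined.

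A reader might infer more than the document supports:
- **Unequal infusion volumes and a broken blind.** Section 6.1.2 says "both caffeine drugs will be dissolved in 40 mLs of dextrose 5% in water". Read literally, the high-dose infusion at 130 kg on the base reading would be 40 + 39 = 79 mL. Section 6.2.4, however, explicitly makes up to a total of 40 mL, the product is already a solution, and the largest stock volume of 39 mL fits within 40 mL. The looser phrase is most naturally shorthand for that instruction. No section says that volumes differ between arms.
- **A wrong power calculation.** Section 9.2 computes power from delirium incidences. Dose is not an input. The unit affects only how well the cited preliminary range supports those incidences, and the unit of that range is itself unstated.
- **Wrong doses already dispensed.** Nothing in the protocol shows that any drug has been dispensed.

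**Conclusion.** The protocol is inconsistent as written. The same two figures denote citrate in the synopsis and base in section 6.1.2, and by the protocol's own equivalence these differ by a factor of two: 0.75 and 1.5 mg/kg base against 1.5 and 3 mg/kg base, or 195 against 390 mg base for the high dose at 130 kg. The result rests only on the 20 mg to 10 mg equivalence in section 6.2.2 and on reading both dose statements as they stand.

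No other section resolves it, and this review takes no position on which dose is intended. The finding does not extend to the power calculation, the blind or past dispensing. It needs correction because it concerns the definition of the intervention. The 40 mL wording is a minor editorial point.

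**What to change.** 1. The sponsor and research pharmacy should reconcile section 1.1 with section 6.1.2 and state the doses in one unit, either caffeine base or caffeine citrate.
2. Use that unit wherever a dose appears (sections 1.1, 4.1, 4.3, 5.2, 6.1.2 and 6.3) and in the preparation instruction in section 6.2.4. Show the citrate/base equivalent once, next to the dose.
3. State the unit of the preliminary dose range in section 9.2, so that it can be compared with the trial doses.
4. As a minor point, align the 40 mL wording in section 6.1.2 with the total volume in section 6.2.4.

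The cost is a protocol amendment limited to wording, with IRB approval, and a check that the pharmacy's preparation documents carry the same unit. The design, sample size and analysis do not change.

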1.2 SCHEMA

The Caffeine, Postoperative Delirium, And CHange IN Outcomes after Surgery-2 (CAPACHINOS-2) Study Protocol <2.0>

Version <2.0>
<14 December 2022>

1.3 SCHEDULE OF ACTIVITIES (SOA)

	Screening/ Enrollment Visit Day -14 to +1	Day of Surgery Visit 1, Day 1	Visit 2 Day 2 POD1 AM	Visit 3 Day 2 POD1 PM	Visit 4 Day 3 POD2 AM	Visit 5 Day 3 POD2 PM	Visit 6 Day 4 POD3 AM	Visit 7 Day 5 POD3 PM	Day 30
Procedures									
Informed consent	X								
Demographics	X								
Medical history	X								
Randomization		X							
Administer study intervention ^a		X	X		X				
Concurrent medication review	X	X	X	X	X	X	X	X	
Physical exam	X	X	X	X	X	X	X	X	
Vital signs	X	X	X	X	X	X	X	X	
Height	X	X							
Weight	X	X							
Cognitive function	X								X
Delirium assessments	X	X	X	X	X	X	X	X	
RASS Score		X	X	X	X	X	X	X	
Quality of Recovery								X	
PONV		X		X		X			
Headache assessments	X	X	X	X	X	X	X	X	
Opioid consumption data	X	X	X	X	X	X	X	X	
Dietary caffeine intake	X	X	X	X	X	X	X	X	
Physical function	X								X
Safety outcomes		X	X	X	X	X	X	X	X
Hospital length of stay and disposition									X
Adverse event review and evaluation	X	X	X	X	X	X	X	X	X
Complete Case Report Forms (CRFs)	X	X	X	X	X	X	X	X	X

On the day of surgery, assessments will occur one hour after postanesthesia care unit admission. Postoperative day (POD) assessments will occur between 7:00 – 10:00 AM, and afternoon assessments will occur between 3:00 – 6:00 PM. Outcomes will be ascertained either via in-person data collection or chart review as outlined in **Section 8.1, Efficacy Assessments**. ^aA research nurse or physician assistant will oversee the drug administration and monitor blood pressure (every 5 minutes), heart rate, heart rhythm (via 5-lead electrocardiography), and continuous pulse oximetry. ^bSee **Sections 8.2 and 9.4.4** for safety outcomes and assessments. Of note, primary and secondary outcomes are primarily reported in this table. Lastly, the 30-day visit can be conducted virtually and/or by telephone as well.

The Caffeine, Postoperative Delirium, And CHange IN Outcomes after Surgery-2 (CAPACHINOS-2) Study Protocol <2.0>

Version <2.0>
<14 December 2022>

2 INTRODUCTION

2.1 STUDY RATIONALE

Delirium is a syndrome characterized by failure of basic cognitive functions that affects approximately 20-50% of older surgical patients.^{5,6} Delirium during surgical recovery is associated with increased mortality,⁷ cognitive and functional decline,^{8,9} and prolonged hospitalization.¹⁰ In fact, 3-year survival rates for acutely hospitalized patients with delirium, and subsyndromal delirium, are both less than 50%.¹¹ Delirium also creates a substantial economic burden, with total healthcare cost estimates ranging from \$38 – \$152 billion annually.¹² Older age is predictive of delirium after surgery,¹³⁻¹⁵ and with aging surgical populations, the incidence of postoperative delirium and related complications are likely to increase in the coming years.

Caffeine represents a novel, neurobiologically informed candidate intervention for reducing risk of early postoperative delirium. Caffeine promotes arousal via adenosine receptor antagonism¹⁶ and improves cognitive function concurrent with increased cortical cholinergic tone.¹⁷⁻¹⁹ Our preliminary data suggest that caffeine reduces risk of postanesthesia care unit (PACU) delirium in adult non-cardiac surgery patients by optimizing cortical dynamics for cognition.^{20,21} Caffeine also optimizes key neurocognitive processes that support information processing²²⁻²⁴ and may improve other, related aspects of clinical recovery, such as rebound headache in habitual caffeine users.²⁵ The objective of this trial is to thus test the effects of caffeine on neurocognitive and clinical recovery after major surgery. Specifically, the primary hypothesis is that caffeine will reduce the incidence of postoperative delirium. The secondary objectives are to (1) test whether caffeine positively impacts the quality of postoperative recovery via validated patient-reported measures and (2) identify neural correlates of delirium and Mild Cognitive Impairment via advanced electroencephalographic (EEG) analysis).

2.2 BACKGROUND

Basic science data demonstrate that caffeine promotes wakefulness via adenosine A_{2A} receptor antagonism,¹⁶ and caffeine also improves arousal and cognitive function via increased cortical cholinergic tone (Fig. 1).¹⁷⁻¹⁹ Caffeine also confers acute anti-nociceptive properties and mitigates risk of postoperative mechanical pain hypersensitivity in a rat model.²⁶ This is highly relevant to the early postoperative setting, as pain is a common postoperative complication that can impair cognitive function in older adults.^{27,28}

In a rat model, Wang et al. demonstrated that caffeine accelerated recovery from both propofol and isoflurane anesthesia in a dose-dependent manner.²⁹ This acceleration, across two different anesthetic classes, occurred without significant changes in hemodynamic physiology. This work was recently translated to healthy volunteers, where caffeine was also found to accelerate emergence time from isoflurane anesthesia (>40% reduction).³⁰ Participants emerged from anesthesia at higher expired isoflurane concentrations and were able to participate in

[figure not shown]

Fig. 1. Caffeine increases cholinergic output from the basal forebrain and laterodorsal tegmentum and pedunculopontine tegmentum via adenosine receptor antagonism. Increased cortical cholinergic tone leads to arousal and improved cognitive function.

The Caffeine, Postoperative Delirium, And CHange IN Outcomes after Surgery-2 (CAPACHINOS-2) Study Protocol <2.0>

Version <2.0>
<14 December 2022>

psychomotor testing earlier upon receiving caffeine. Encouragingly, no statistically significant differences in cardiac or pulmonary physiologic recovery patterns were appreciated.

A recent single-center clinical trial was designed to test the effects of caffeine on early neurocognitive recovery after major laparoscopic surgery in adults.²⁰ Results demonstrated that caffeine significantly reduced the risk of PACU delirium (Fig. 2). However, PACU delirium was a post-hoc, exploratory outcome, with a low fragility index³¹ between placebo and caffeine groups. Nonetheless, patients randomized to caffeine also demonstrated increased neurophysiologic signs of arousal based on EEG analysis in the PACU.²⁰ A secondary analysis of the EEG data demonstrated increased neurophysiologic *criticality*, which reflects a point of dynamic instability that may allow for flexible access to a wide range of brain states (and thus, improved cognitive function).²¹ Lastly, in this trial, caffeine was not found to reduce opioid consumption, subjective pain reporting, or anesthetic emergence time. However, the small sample size (n=65) precludes firm conclusions. Of note, no major adverse events were reported in relation to caffeine, and early postoperative hemodynamic recovery patterns were similar compared to placebo.

[figure not shown]

Fig. 2. PACU delirium was significantly reduced in patients receiving intravenous caffeine (4/33, 12%) compared to placebo (10/30, 33%; $p=0.04$) during surgical closure.

Three previous single-center clinical trials were also designed to test the effects of caffeine on postoperative recovery profiles. A trial by Weber et al. demonstrated a reduced risk of postoperative headache in ambulatory surgery patients at risk for withdrawal headaches (based on baseline intake) after receiving caffeine compared to placebo (10% vs. 23%, $p<0.05$).²⁵ No difference was noted in terms of PACU recovery time. Steinbrook et al. studied the effects of caffeine on postoperative nausea and vomiting, finding that caffeine was associated with an increased risk of nausea (26% vs. 10%, $p=0.02$), but no statistically significant difference was found for the incidence of vomiting, rescue antiemetic use, headaches, fatigue, time to discharge or satisfaction scores (0-10 ordinal scale).³² Between these two trials, multiple (and relevant) outcomes were not studied, such as anesthetic emergence time, perioperative neurocognitive function, opioid consumption, comprehensive pain measures, or overall patient-reported quality of recovery using rich, multidimensional scales with validation and minimal clinically important difference data.³³⁻³⁵ Furthermore, these trials were

restricted to outpatient surgery, so the aforementioned outcomes were not studied for inpatient surgery. Lagier and colleagues performed a single-center randomized trial to determine whether caffeine reduces postoperative atrial fibrillation in cardiac surgery patients.³⁶ Caffeine was administered every eight hours (400 mg tablets orally or via nasogastric tube) for a total of six doses. Caffeine did not reduce atrial fibrillation incidence, but, importantly, major adverse events (e.g., arrhythmias, renal injury, hypoxemia) were similar to the placebo group. Postoperative nausea and vomiting risk was higher in the caffeine group compared to placebo (27% vs. 7%, respectively, $p=0.005$).

Overall, there are converging clinical-translational data to suggest that caffeine may enhance postoperative neurocognitive recovery. However, previous clinical trials have not focused on delirium as the primary outcome, nor have they incorporated tools such as EEG to determine how caffeine might affect underlying cortical dynamics during surgical recovery. The proposed trial will address these gaps; delirium will be the prespecified primary outcome, measured by a validated assessment tool (see

The Caffeine, Postoperative Delirium, And CHange IN Outcomes after Surgery-2 (CAPACHINOS-2) Study Protocol <2.0>

Version <2.0>
<14 December 2022>

Section 8.1, Efficacy Assessments), and a high-density, whole-scalp EEG system will be used to elucidate cortical dynamics during early postoperative recovery.

2.3 RISK/BENEFIT ASSESSMENT

2.3.1 KNOWN POTENTIAL RISKS

Contraindications, drug interactions, and adverse reactions are described in the caffeine citrate package insert (<https://dailymed.nlm.nih.gov/dailymed/drugInfo.cfm?setid=38b39044-737a-4247-a6c4-c86f5e92490e&audience=consumer>). Primary risks described relate to the pediatric (neonatal) population, which will not be included in this trial.

In the acute setting, caffeine has been associated with various side effects. As mentioned previously, Steinbrook et al. demonstrated that perioperative caffeine may increase the risk of nausea, though participants randomized to caffeine experienced neither an increased risk of vomiting nor increased rescue antiemetic use.³² Lagier et al. also demonstrated that postoperative caffeine may increase nausea and vomiting risk; however, the dose and frequency used (400 mg every eight hours, six total doses) are higher than the current trial.³⁶ Additional safety data have been published in various adult settings. McLellen et al. provide a thorough review of the adult literature relating to caffeine use and side effects.³⁷ The following side effects and risks of acute caffeine intake have been documented:

- Anxiety
- Irritability
- Gastrointestinal distress
- Tremors
- Nervousness
- Sleep disruption

Side effects have generally occurred with relatively high doses (600 mg)^{38,39} and/or in participants with excessive sensitivity (e.g., genetic polymorphisms, non-regular consumers).^{40,41} Case reports have demonstrated associations between caffeine intake and increased seizure frequency, particularly in the setting of (1) relatively high doses and (2) pre-existing history of epilepsy.^{42,43} A subsequent large population-based study did not reveal an adjusted association with habitual caffeine intake and seizure history.⁴⁴ Whether caffeine acts as a common seizure trigger is unclear,⁴⁵ but additional precipitating factors (e.g., sleep disturbances) are common in the perioperative setting⁴⁶ which may exacerbate epileptiform activity and seizure risk.

The effects of acute caffeine intake on cardiac arrhythmia risk have also been studied for several years across diverse patient populations. The table below summarizes studies examining acute caffeine administration in relation to cardiovascular physiologic perturbations.

Year	Authors	Sample size (n)	Description
1983	Dobmeyer DJ et al.	19	Caffeine (200 mg) modulated atrial refractory periods, but conduction intervals remained unchanged. Two participants receiving caffeine experienced non-sustained ventricular tachycardia after programmed ventricular stimulation, and six participants experienced sustained supraventricular

The Caffeine, Postoperative Delirium, And CHange IN Outcomes after Surgery-2 (CAPACHINOS-2) Study Protocol <2.0>

Version <2.0>
<14 December 2022>

			tachycardia after caffeine and programmed stimulation.
1987	Myers MG et al.	70	No association with caffeine (300 mg) and ventricular ectopic activity in patients with a recent myocardial infarction. Increases in plasma catecholamines, systolic blood pressure (116 ± 2 vs. 123 ± 2 mmHg), and diastolic blood pressure (70 ± 1 mmHg vs. 74 ± 1 mmHg); no changes in heart rate observed.
1989	Graboyes TB et al. ⁴⁷	50	No association with caffeine (200 mg) and ventricular arrhythmia risk during exercise in patients with malignant ventricular arrhythmia history. Increased catecholamine levels appreciated up to 3 hours after caffeine administration.
1990	Myers MG and Harris L ⁴⁸	35	No association with caffeine (450 mg) and ventricular arrhythmias in patients with recent myocardial infarction.
1990	Chelsky LB et al. ⁴⁹	22	In patients with ventricular arrhythmia history, caffeine (275 mg) did not significantly alter the inducibility or severity of ventricular arrhythmias.
2018	Lagier et al. ³⁶	55 (caffeine arm)	Randomized clinical trial to determine whether perioperative caffeine would reduce the incidence of postoperative atrial fibrillation. Caffeine (400 mg) was administered orally or via nasogastric tube, beginning intraoperatively and every eight hours thereafter for six total doses. Major adverse events (e.g., atrioventricular block, hypoxemia, renal injury) were similar between placebo and caffeine groups.
2002	Corti R et al. ⁵⁰	15	Both coffee and caffeine (275 mg) increased sympathetic nerve activity and systolic blood pressure (6.4 ± 1.7 mm Hg) one hour after administration. Heart rate decreased (-4.6 ± 2 bpm) one hour after administration.
2015	Lemery R et al. ⁵¹	80	No association with oral caffeine (5 mg/kg) and supraventricular tachycardia risk in patients with prior history. Furthermore, caffeine did not modulate refractory periods or nodal conduction. Caffeine was associated with increase systolic ($143 [128-165]$ mmHg vs. $132 [114-150]$ mmHg) and diastolic ($83 [77-94]$ mmHg vs. $74 [69-86]$ mmHg) blood pressure. Heart rate remained unchanged.

The CAffeine, Postoperative Delirium, And CHange IN Outcomes after Surgery-2 (CAPACHINOS-2) Study Protocol <2.0>

Version <2.0>
<14 December 2022>

2016	Dixit S et al. ⁵²	1388	No association between habitual caffeine consumption and premature ectopic beats during a 24-hour holter monitoring period.
2016	Zuchinali P et al. ⁵³	51	In patients with moderate-to-severe left ventricular systolic dysfunction, caffeine (500 mg) was not associated with risk of new arrhythmias.

Importantly, these data suggest that acute caffeine intake is not associated with adverse cardiovascular events, even in the setting of pre-existing cardiac pathology (e.g., recent myocardial infarction, ventricular arrhythmia history, recent coronary artery bypass surgery). Acute caffeine administration may lead to increased serum catecholamine levels and modest increases in blood pressure.

In the perioperative setting, caffeine has been studied in relation to perioperative headache, nausea and vomiting risk, gastrointestinal function, and, in the cardiac population, risk of new-onset atrial fibrillation.

Year	Authors	Sample size (n)	Description
1993	Weber et al. ⁵⁴	105 (caffeine arm)	Observational study to determine whether habitual (oral) caffeine intake, on the day of surgery, would reduce the incidence and severity of perioperative headache. Caffeine intake was associated with reduced headache incidence. Adverse events were not reported in the study.
1995	Hampl et al. ⁵⁵	20 (caffeine arm)	Randomized clinical trial, whereby habitual caffeine users were randomized to caffeine tablets (dose matched to daily intake) or placebo on the day of surgery and on the first postoperative morning. Perioperative headache was significantly reduced in patients randomized to caffeine. Adverse events were not reported.
1997	Weber et al. ²⁵	114 (caffeine arm)	The trial objective was to determine whether caffeine would mitigate risk of postoperative headache and reduce recovery time. Patients were randomized to intravenous caffeine (200 mg) or placebo administered in the PACU upon admission. Habitual users were less likely to experience a postoperative headache if randomized to caffeine. Adverse events were not reported in the trial.
2013	Steinbrook et al. ³²	62 (caffeine arm)	The trial objective was to determine whether intravenous caffeine sodium benzoate (500 mg), given 15 minutes prior to anesthetic emergence, would reduce risk of postoperative nausea or vomiting during outpatient surgery. Nausea was more common in the caffeine group, and

The Caffeine, Postoperative Delirium, And CHange IN Outcomes after Surgery-2 (CAPACHINOS-2) Study Protocol <2.0>

Version <2.0>
<14 December 2022>

			caffeine did not improve headache, fatigue, satisfaction, or time to discharge. Adverse events were not reported in the trial.
2018	Lagier et al. ³⁶	55 (caffeine arm)	Randomized clinical trial to determine whether perioperative caffeine would reduce the incidence of postoperative atrial fibrillation. Caffeine (400 mg) was administered orally or via nasogastric tube, beginning intraoperatively and every eight hours thereafter for six total doses. Major adverse events (e.g., atrioventricular block, hypoxemia, renal injury) were similar between placebo and caffeine groups.
2021	Liu et al. ⁵⁶	40 (caffeine arm)	Adult gastrointestinal surgery patients demonstrated improved recovery time of gastrointestinal function with randomization to daily green tea postoperatively. No adverse events reported.
2021	[name] et al. ²⁰	33 (caffeine arm)	Non-cardiac surgery patients receiving intravenous caffeine (200 mg) during surgical closure demonstrated reduced PACU delirium. No major adverse events in relation to caffeine. Furthermore, postoperative hemodynamic recovery profiles were similar compared to placebo patients.

In summary, perioperative caffeine administration is associated with reduced headache in habitual caffeine users. Caffeine may also increase the risk of postoperative nausea and/or vomiting. Both intravenous and oral administration routes have been utilized. Adverse events were not reported in many of these studies, though no major adverse events were reported based on available data.

In the chronic setting, caffeine has also been studied in relation to cardiovascular health and outcomes. Major, representative studies are outlined below:

Year	Authors	Sample size (n)	Description
1999	de Vreede-Swagemakers JJ et al. ⁵⁷	117	>10 cups of coffee per day was associated with sudden cardiac arrest in patients with coronary artery disease
2005	Frost L and Vestergaard p ⁵⁸	47,949	No association between caffeine consumption and risk of atrial fibrillation or flutter
2006	Lopez-Garcia E et al. ⁵⁹	128,493	No association between coffee consumption and coronary heart disease
2010	Reis JP et al. ⁶⁰	5,115	No substantial association between coffee or caffeine intake and coronary and carotid atherosclerosis

The Caffeine, Postoperative Delirium, And CHange IN Outcomes after Surgery-2 (CAPACHINOS-2) Study Protocol <2.0>

Version <2.0>
<14 December 2022>

2011	Klatsky AL et al. ⁶¹	130,054	An inverse relationship was demonstrated between habitual caffeine intake and hospitalization for arrhythmias
------	---------------------------------	---------	---

Chronic caffeine consumption does not appear to be associated with adverse cardiovascular outcomes in the non-surgical setting.

Overall, the weight of available evidence suggests that caffeine administration is not associated with major adverse cardiovascular perturbations (in both acute and chronic settings), particularly at moderate doses consistent with those chosen for this trial. In the perioperative setting, caffeine may reduce risk of rebound headache in habitual users, though caffeine has also been associated with increased postoperative nausea and vomiting. Additional side effects, such as tremors, nervousness, gastrointestinal distress, anxiety, irritability, and sleep disruption remain possible.

